#### **2.1.4.1 Hypoglycemia**

Hypoglycemia will be identified as events recorded on the dedicated e-CRF “Hypoglycemic event information” page, and will be categorized as follows (see study protocol for further details):

##### **Severe hypoglycemia**

Severe hypoglycemia is an event requiring assistance of another person to actively administer carbohydrate, glucagon, intravenous glucose or other resuscitative actions. These episodes may be associated with sufficient neuroglycopenia to induce seizure, unconsciousness or coma.

Self-monitored plasma glucose values may not be available, but neurological recovery attributable to the restoration of plasma glucose to normal is considered sufficient evidence that the event was induced by a low plasma glucose concentration.

Severe hypoglycemia is identified in e-CRF “Hypoglycemic event information” page as those documented as,

1. To the question “Countermeasure Administration”, ticked the option “Subject was Not Capable of Treating Self and Required Assistance”, and
2. To the question “Were Symptoms Present”, ticked “Yes”.

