10.6.1 Hypoglycemia

During the study, patients are instructed to document any hypoglycemic episodes in their study diary. The hypoglycemia will be reported in the specific e-CRF page with onset date and time, symptoms and/or signs, the SMBG value if available, and the treatment. If the event fulfills SAE criteria, the hypoglycemia will also be reported as an SAE.

Hypoglycemia is categorized according to the ADA workgroup on hypoglycemia classification (12)(13) and summarized in [Figure 1](#).

In addition to the threshold of ≤ 3.9 mmol/L (≤ 70 mg/dL), hypoglycemia episodes with a plasma glucose of < 3.0 mmol/L (< 54 mg/dL) will be analyzed separately.

Figure 1 - Hypoglycemia classification in Study EFC14835

*The patient is not able to treat her/himself because of the acute neurological impairment and requires another person to actively administer sugar, glucagon or intravenous glucose

PG: plasma glucose; SAE: serious adverse event.

Severe hypoglycemia

Severe hypoglycemia is an event requiring assistance of another person to actively administer carbohydrate, glucagon, intravenous glucose or other resuscitative actions. These episodes may be associated with sufficient neuroglycopenia to induce seizure, unconsciousness or coma. Self-monitored plasma glucose values may not be available, but neurological recovery attributable to the restoration of plasma glucose to normal is considered sufficient evidence that the event was induced by a low plasma glucose concentration.

Note: “requiring assistance of another person” means that the patient could not help himself or herself to treat the hypoglycemia. Assisting a patient out of kindness, when assistance is not required, should not be considered a “requires assistance” incident.

Any hypoglycemic event which leads to unconsciousness, coma, or seizure should also be reported as an **SAE**.

Documented symptomatic hypoglycemia

Documented symptomatic hypoglycemia is an event during which typical symptoms of hypoglycemia accompanied by a measured plasma glucose concentration of ≤ 3.9 mmol/L (≤ 70 mg/dL).

Clinical symptoms that are considered to result from a hypoglycemic episode are eg, increased sweating, nervousness, asthenia/weakness, tremor, dizziness, increased appetite, palpitations, headache, sleep disorder, confusion, seizures, unconsciousness, or coma.

Asymptomatic hypoglycemia

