### **Asymptomatic hypoglycemia**

Asymptomatic hypoglycemia is an event not accompanied by typical symptoms of hypoglycemia but with a measured plasma glucose concentration  $\leq 3.9$  mmol/L ( $\leq 70$  mg/dL).

Asymptomatic hypoglycemia is identified in e-CRF “Hypoglycemic event information” page as those documented as:

1. To the question “Countermeasure Administration”, NOT ticked the option “Subject was Not Capable of Treating Self and Required Assistance”, and,
2. To the question “Were Symptoms Present”, ticked “No”, and,
3. With a plasma glucose value before countermeasure  $\leq 3.9$  mmol/L ( $\leq 70$  mg/dL).

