### **Relative hypoglycemia**

Relative hypoglycemia, recently termed “pseudo hypoglycemia”, is an event during which the patient reports typical symptoms of hypoglycemia, and interprets the symptoms as indicative of hypoglycemia, but with a measured plasma glucose concentration  $>3.9$  mmol/L ( $>70$  mg/dL).

Relative hypoglycemia is identified in e-CRF “Hypoglycemic event information” page as those documented as,

1. To the question “Countermeasure Administration”, NOT ticked the option “Subject was Not Capable of Treating Self and Required Assistance”,
2. To the question “Were Symptoms Present”, ticked “Yes”, and,
3. With a plasma glucose value before countermeasure  $>3.9$  mmol/L ( $>70$  mg/dL).

In addition of the threshold of  $\leq 3.9$  mmol/L ( $\leq 70$  mg/dL), hypoglycemia episodes with a plasma glucose of  $<3.0$  mmol/L ( $<54$  mg/dL) will be analyzed separately.

Any hypoglycemic event fulfilling the criteria of a SAE or leading to unconsciousness, coma, or seizure will also be recorded as a SAE (Section 2.1.4.2).

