Stroke	Positively adjudicated by CEC: Yes to the question "Does the event meet the definition of a Stroke for this study?"
Heart failure requiring hospitalization	Positively adjudicated by CEC: Yes to the question "Does the event meet the definition of a Heart Failure Event for this study?"
Bone fractures	Positively adjudicated by CEC: Yes to the question "Did the Fracture occur?"
Diabetic ketoacidosis	Positively adjudicated by CEC: Yes to the question "Does this event meet the criteria to be a DKA event?"
EOSI Renal events where select events adjudicated	
Sustained ≥50% decrease in eGFR	(1) For ≥50% decrease in eGFR from baseline, (1a) confirmed ≥50% decrease in GFR for ≥30 days with no reversible cause as recorded in e-CRF "eGFR decrease", OR (1b) positively adjudicated by CEC: Yes to the question "Does the subject meet the criteria of CKD progression" for ≥50% decrease in eGFR.
Sustained eGFR <15 mL/min/1.73 m 	(2) For eGFR <15 mL/min/1.73 m  , (2a) confirmed eGFR <15 mL/min/1.73 m  for ≥30 days with no reversible cause as recorded in e-CRF "eGFR decrease", OR (2b) positively adjudicated by CEC: Yes to the question "Does the subject meet the criteria of CKD progression".
Chronic dialysis	(3) For dialysis, (3a) dialysis lasted for ≥90 days (eg, end date – start date+ 1 ≥90) as recorded in e-CRF "Renal Event – Dialysis", OR (3b) positively adjudicated by CEC: Yes to the question ". Does the subject meet the criteria for ESRD".
Renal transplant*	(4) "Renal transplant" captured in e-CRF "Other procedure form", where adjudication is not required. PTs of Renal transplant (10038533), Renal and pancreas transplant (10052278), Renal and liver transplant (10052279) based on MedDRA v22.0.
Renal death	(5) Renal death as positively adjudicated by CEC: "Death - Non-Cardiovascular (Renal)" as the primary cause of death

AE Grouping	Criteria
EOSI not adjudicated*	
Severe hypoglycemia	Algorithm specified in Section 2.1.4.1 based on e-CRF "Hypoglycemic Events"
Genital mycotic infections	PTs in Appendix B
Urinary tract infections	PTs in Appendix B
Clinically relevant volume depletion and events related/possibly related to volume depletion	PTs in Appendix B

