#### **2.4.5.1 Analyses of hypoglycemia**

Analyses of hypoglycemia will be performed on the TEAE periods as defined in [Section 2.1.4](#). Hypoglycemia will be classified as severe hypoglycemia, documented symptomatic hypoglycemia, asymptomatic hypoglycemia, probable symptomatic hypoglycemia or relative hypoglycemia [Section 2.1.4.1](#).

The number (%) of patients with any hypoglycemia, severe hypoglycemia, and documented symptomatic hypoglycemia will be summarized respectively by treatment group during the TEAE period, as well as the incidence rate in patient years. Two types of incidence rates will be presented: the number of patients with at least 1 event per 100 patient years (calculated as the number of patients with at least 1 event / total exposure in 100 patient years), and the number of events per 100 patient-years [calculated as the total number of events / (total exposure in 100 patient-years)]. Note: here exposure (in days) is duration of TEAE period, ie, duration of IMP treatment in days +1 (Section 2.1.4).

The summary of frequency and incidence rate in patient years for severe hypoglycemia or documented symptomatic hypoglycemia will be provided as appropriate by gender (Male, Female), age group (<50, ≥50 to <65, ≥65 years), race (White, Black or African American, Asian, Other) and Metformin use at Screening (Yes, No).

A KM curve will also be provided by treatment group for the time to first severe hypoglycemia or documented symptomatic hypoglycemia during the TEAE period for the 79-week entire treatment period only.

Documented symptomatic hypoglycemia maybe presented by  $\leq 3.9$  mmol/L ( $\leq 70$  mg/dL) and  $< 3.0$  mmol/L ( $< 54$  mg/dL) respectively, as appropriate.

A listing of patients for all events reported on the dedicated e-CRF “Hypoglycemic event information” page will be provided with each category flagged (ie, severe hypoglycemia, documented symptomatic hypoglycemia, asymptomatic hypoglycemia, probable symptomatic hypoglycemia and relative hypoglycemia).

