#### *Other EOSIs*

For EOSIs that are not adjudicated, the number (%) of patients with at least one event will be summarized by treatment group and by PT (as identified in [Table 3](#) in [Section 2.1.4.2](#)).

Severe hypoglycemia will be included in the summary of hypoglycemia (See [Section 2.5.1](#)).

AE leading to an amputation is described in the section below.

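### The SAP's severe hypoglycemia rule adds a symptoms tick that the text definition lacks, so an assisted event with symptoms No or blank falls in no category

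*SAP*

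**What the plan says.** Protocol 10.6.1 gives the text definition: "Severe hypoglycemia is an event requiring assistance of another person to actively administer carbohydrate, glucagon, intravenous glucose or other resuscitative actions". SAP 2.1.4.1 repeats it. Neither text sets a symptom condition. Both say that neuroglycopenia may accompany such an episode and that a glucose value may be unavailable.

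SAP 2.1.4.1 then states how the event is identified on the hypoglycemia page of the e-CRF. Two conditions are joined by 'and': the option that the subject could not treat themselves and needed assistance is ticked, and "To the question “Were Symptoms Present”, ticked “Yes".

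The same algorithm serves the event of special interest. SAP Table 3 gives the criterion for severe hypoglycemia as "Algorithm specified in Section 2.1.4.1 based on e-CRF" (hypoglycemic events page), and SAP 2.4.5.2 (Other EOSIs) says "Severe hypoglycemia will be included in the summary of hypoglycemia". SAP 2.4.5.1 uses the category for the number and percentage of patients, two incidence rates per 100 patient-years, subgroup summaries, and a Kaplan-Meier curve "for the time to first severe hypoglycemia or documented symptomatic hypoglycemia during the TEAE period".

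**The concern.** The definition has one element, assistance. The derivation has two. Measured against the SAP's own text, the second condition can only remove events from the severe category and can never add one. An event removed this way is not downgraded to a milder category, because every milder category excludes assisted events. It is left unclassified.

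Severe hypoglycemia is an event of special interest in the protocol. Protocol 4.2 names a possible increase in hypoglycemia when the drug is given with insulin or an insulin secretagogue such as a sulfonylurea, which is the background therapy here. A count of severe events that depends on how a second box was completed is a weak basis for describing that risk.

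**Working it through.** This is a check of logic; the plan states no figure to reproduce. The five rules in SAP 2.1.4.1, side by side:

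| Category | Assistance option | Symptoms present | Glucose before countermeasure (mmol/L) | Other |
|---|---|---|---|---|
| Severe | ticked | Yes | no condition | none |
| Documented symptomatic | not ticked | Yes | ≤3.9 | none |
| Asymptomatic | not ticked | No | ≤3.9 | none |
| Probable symptomatic | not ticked | Yes | no value | prompt recovery Yes |
| Relative | not ticked | Yes | >3.9 | none |

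Now take an event with assistance ticked.

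1. Symptoms Yes: severe, at any glucose value or none.
2. Symptoms No: fails the severe rule on its second condition. The asymptomatic rule is the only one that accepts "To the question “Were Symptoms Present”, ticked “No", and it fails there because assistance is ticked. No category, even with glucose ≤3.9.
3. Symptoms blank: fails the severe rule in the same way, and fails the other four on assistance. No category.

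The glucose value and the recovery answer do not change results 2 and 3. Nor is the second condition a check that glucose was low. An assisted event with symptoms Yes and glucose >3.9 is severe, while one with symptoms No and glucose ≤3.9 is unclassified.

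No later rule repairs this. For hypoglycemia records, SAP 2.5.3 covers missing dates and times only; it has no rule for a blank symptoms item. Elsewhere the SAP treats missing safety data conservatively: an unclear onset date defaults to treatment-emergent, and a missing relationship to IMP is taken as related. Here a blank removes an assisted event from the most serious category.

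If severe is derived from the assistance tick alone, every assisted event is severe. None falls in two categories, because the other four rules require assistance not ticked.

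Scale of a single event, as a unit and not an estimate of loss (arm size from SAP 1.3):

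- One patient: 1/250 = 0.40 percentage points.
- Core period, 182 days, all 250 exposed throughout (assumption): 250 × 182/365.25 = 124.6 patient-years, so one event is 100/124.6 = 0.80 per 100 patient-years. With 80% of that exposure (assumption): 99.7 patient-years and 1.00.
- Entire period, 551 + 1 days: 250 × 552/365.25 = 377.8 patient-years and 0.26. With 80%: 302.3 patient-years and 0.33.

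**The case against.** The strongest reply is that the second condition implements the definition. The Figure 1 footnote in Protocol 10.6.1 reads "The patient is not able to treat her/himself because of the acute neurological impairment", and the symptom list for documented symptomatic hypoglycemia includes confusion, seizures, unconsciousness and coma. On a correctly completed form, a patient unable to self-treat has symptoms, so assistance with symptoms No is mainly a contradictory record. The second tick may also guard against help given out of kindness, which the protocol excludes. This stands as a reason to expect few such records. It does not justify the condition: on correct forms it changes nothing, and on inconsistent or blank forms it loses the event.

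Figure 1 is not shown in the text reviewed and may branch on symptoms. If it does, the SAP follows the protocol and the text definitions are what is incomplete. The affected events would still have no category. The e-CRF is also unseen, so an edit check may already prevent a blank. Protocol 13.4 provides for data queries in general, but neither document names a check for this inconsistency.

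A reader might infer that severe events vanish from the report. The documents do not support that. SAP 2.4.5.1 lists every event on the hypoglycemia page with its category flagged. On the natural reading of SAP 2.1.4.1, all of them count as any hypoglycemia. The SAP also states: "Any hypoglycemic event fulfilling the criteria of a SAE or leading to unconsciousness, coma, or seizure will also be recorded as a SAE". Under Protocol 10.4.5 a non-serious event of special interest is reported as an AE. Those AE and SAE tables are by system organ class and preferred term, so they keep the event visible but do not restore the severe count.

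**Conclusion.** The point holds as a gap between definition and derivation. An assisted event with symptoms No or blank is unclassified and is missing from the severe number and percentage, both rates, the subgroup summaries, the Kaplan-Meier curve and the event of special interest.

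The size is probably small and cannot be estimated. The exposure is limited to contradictory or blank ticks, and the documents give neither their frequency nor an expected number of severe events. The number of tick combinations left unclassified says nothing about how many events are affected. Safety analyses are descriptive, so no hypothesis test is at stake.

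A reader might also infer that the rule favors sotagliflozin. Nothing in the documents supports a direction: the rule is the same in both arms, and where inconsistent ticks would fall is unknown.

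The conclusion assumes that the text definition governs unless Figure 1 states otherwise, and that the e-CRF allows the combination to be recorded.

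**What to change.** 1. Before database lock, query every assisted event with symptoms No or blank.
2. Reconcile the derivation in SAP 2.1.4.1 with the text definition and Protocol Figure 1. Unless Figure 1 states a symptom condition, derive severe hypoglycemia from the assistance tick alone. Do not substitute a glucose condition: the definition has none, and it says that glucose may be unavailable.
3. Show, as a sensitivity count, the severe events that also have symptoms Yes.
4. If Figure 1 does state a symptom condition, add it to the text definition and report assisted events that fail it in a separate row, so that none is unclassified.

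The cost is one derivation rule, one query and one extra table row, all from data already collected. The downside is that an assistance box ticked in error counts as severe unless the query corrects it. The protocol note on help given out of kindness reduces that risk, and the sensitivity count shows how far the result depends on it.

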##### **Documented symptomatic hypoglycemia**

Documented symptomatic hypoglycemia is an event during which typical symptoms of hypoglycemia accompanied by a measured plasma glucose concentration of  $\leq 3.9$  mmol/L ( $\leq 70$  mg/dL).

Clinical symptoms that are considered to result from a hypoglycemic episode are eg, increased sweating, nervousness, asthenia/weakness, tremor, dizziness, increased appetite, palpitations, headache, sleep disorder, confusion, seizures, unconsciousness, or coma.

Documented symptomatic hypoglycemia is identified in e-CRF “Hypoglycemic event information” page as those documented as:

1. To the question “Countermeasure Administration”, NOT ticked the option “Subject was Not Capable of Treating Self and Required Assistance”, and,
2. To the question “Were Symptoms Present”, ticked “Yes”, and,
3. With a plasma glucose value before countermeasure  $\leq 3.9$  mmol/L ( $\leq 70$  mg/dL).

### **Asymptomatic hypoglycemia**

Asymptomatic hypoglycemia is an event not accompanied by typical symptoms of hypoglycemia but with a measured plasma glucose concentration  $\leq 3.9$  mmol/L ( $\leq 70$  mg/dL).

Asymptomatic hypoglycemia is identified in e-CRF “Hypoglycemic event information” page as those documented as:

1. To the question “Countermeasure Administration”, NOT ticked the option “Subject was Not Capable of Treating Self and Required Assistance”, and,
2. To the question “Were Symptoms Present”, ticked “No”, and,
3. With a plasma glucose value before countermeasure  $\leq 3.9$  mmol/L ( $\leq 70$  mg/dL).

### **Probable symptomatic hypoglycemia**

Probable symptomatic hypoglycemia is an event during which symptoms of hypoglycemia are not accompanied by a plasma glucose determination, (but that was presumably caused by a plasma glucose concentration  $\leq 3.9$  mmol/L [ $\leq 70$  mg/dL]), ie, symptoms treated with oral carbohydrate without a test of plasma glucose.

Probable symptomatic hypoglycemia is identified in e-CRF “Hypoglycemic event information” page as those documented as,

1. To the question “Countermeasure Administration”, NOT ticked the option “Subject was Not Capable of Treating Self and Required Assistance”, and,
2. To the question “Were Symptoms Present”, ticked “Yes”, and,
3. With no plasma glucose value before countermeasure, and,
4. To the question “Did this countermeasure lead a significant improvement or prompt recovery?”, ticked “Yes”.

### **Relative hypoglycemia**

Relative hypoglycemia, recently termed “pseudo hypoglycemia”, is an event during which the patient reports typical symptoms of hypoglycemia, and interprets the symptoms as indicative of hypoglycemia, but with a measured plasma glucose concentration  $>3.9$  mmol/L ( $>70$  mg/dL).

Relative hypoglycemia is identified in e-CRF “Hypoglycemic event information” page as those documented as,

1. To the question “Countermeasure Administration”, NOT ticked the option “Subject was Not Capable of Treating Self and Required Assistance”,
2. To the question “Were Symptoms Present”, ticked “Yes”, and,
3. With a plasma glucose value before countermeasure  $>3.9$  mmol/L ( $>70$  mg/dL).

In addition of the threshold of  $\leq 3.9$  mmol/L ( $\leq 70$  mg/dL), hypoglycemia episodes with a plasma glucose of  $<3.0$  mmol/L ( $<54$  mg/dL) will be analyzed separately.

Any hypoglycemic event fulfilling the criteria of a SAE or leading to unconsciousness, coma, or seizure will also be recorded as a SAE (Section 2.1.4.2).

#### **2.1.4.2 Adverse events variables**

##### **AE observation period**

- **Pretreatment AEs** are AEs that developed or worsened or became serious from the signed informed consent date up to first administration of double-blind IMP.
- **TEAEs** are AEs that developed or worsened or became serious during the TEAE period.
- **Posttreatment AEs** are AEs that developed or worsened or became serious during the posttreatment period.

All AEs (including SAEs, AESI and EOSI) will be coded to a LLT, PT, HLT, HLGT, and associated SOC using the version of MedDRA currently in effect at Covance at the time of database lock.

The occurrence of AEs (including SAEs, AESI and EOSI) will be recorded from the time of signed informed consent until the end of the study (see Section 2.1.4) or the resolution/stabilization of all SAE, AESI and EOSI.

**AESI** include

- Pregnancy.
- Symptomatic overdose with IMP/NIMP.
- Alanine aminotransferase (ALT) increase  $> 3 \times$  upper limit of normal (ULN).

**EOSI include**

- Major adverse cardiovascular events (MACE [cardiovascular death, myocardial infarction, or stroke]) and other specific cardiovascular (CV) events (eg, heart failure requiring hospitalization).
- Severe hypoglycemia.
- Genital mycotic infections (to include vulvovaginal candidiasis in females and candida balanitis in males).
- Urinary tract infection.
- Clinically relevant volume depletion and events related/possibly related to volume depletion.
- Diarrhea.
- Pancreatitis.
- Bone fractures.
- Venous thrombotic events, to include deep venous thrombosis and thromboembolism (to include pulmonary embolism).
- Diabetic ketoacidosis.
- Renal events, to include 50% decline in eGFR, end stage kidney disease, renal death.
- Malignancies of special interest (breast, bladder, renal cell, Leydig cell, pancreatic, prostate, and thyroid cancer).
- AE leading to an amputation.

A Clinical Endpoint Committee (CEC) will, in a blinded manner, review and adjudicate all deaths, myocardial infarction, stroke, unstable angina requiring hospitalization, and heart failure requiring hospitalization, selected renal events, bone fracture, and diabetic ketoacidosis.

Two independent committees will review safety events that require ongoing monitoring to ensure timing protocol amendments in case a safety signal is identified. These events are: 1) potential cases of drug-induced liver injury (DILI), and 2) cases of amputations. The two committees will review the cases in a treatment-blinded manner and will present their assessment to the DMC.

AESI and EOSI will be identified based on criteria in Table 3.

Table 3 - Criteria for AESI and EOSI

AE Grouping	Criteria
AESI	
Pregnancy	e-CRF "Pregnancy"
Symptomatic overdose with IMP/NIMP	"Overdose of IMP" or "Overdose of NIMP" checked and "Symptomatic overdose" checked in e-CRF "Overdose"
ALT increase >3 × ULN	e-CRF "ALT increase"
EOSI adjudicated	
Cardiovascular death	Positively adjudicated by CEC: "Cardiovascular" or "Undetermined" as the primary cause of death
Myocardial infarction, Unstable Angina requiring hospitalization	Positively adjudicated by CEC: Yes to the question "Does the event meet the definition of an MI for this study?", or Yes to the question "If event is not an MI, does the event meet the definition of an UA Requiring admission to hospital or emergency room, for this study?"
Stroke	Positively adjudicated by CEC: Yes to the question "Does the event meet the definition of a Stroke for this study?"
Heart failure requiring hospitalization	Positively adjudicated by CEC: Yes to the question "Does the event meet the definition of a Heart Failure Event for this study?"
Bone fractures	Positively adjudicated by CEC: Yes to the question "Did the Fracture occur?"
Diabetic ketoacidosis	Positively adjudicated by CEC: Yes to the question "Does this event meet the criteria to be a DKA event?"
EOSI Renal events where select events adjudicated	
Sustained ≥50% decrease in eGFR	(1) For ≥50% decrease in eGFR from baseline, (1a) confirmed ≥50% decrease in GFR for ≥30 days with no reversible cause as recorded in e-CRF "eGFR decrease", OR (1b) positively adjudicated by CEC: Yes to the question "Does the subject meet the criteria of CKD progression" for ≥50% decrease in eGFR.
Sustained eGFR <15 mL/min/1.73 m 	(2) For eGFR <15 mL/min/1.73 m  , (2a) confirmed eGFR <15 mL/min/1.73 m  for ≥30 days with no reversible cause as recorded in e-CRF "eGFR decrease", OR (2b) positively adjudicated by CEC: Yes to the question "Does the subject meet the criteria of CKD progression".
Chronic dialysis	(3) For dialysis, (3a) dialysis lasted for ≥90 days (eg, end date – start date+ 1 ≥90) as recorded in e-CRF "Renal Event – Dialysis", OR (3b) positively adjudicated by CEC: Yes to the question ". Does the subject meet the criteria for ESRD".
Renal transplant*	(4) "Renal transplant" captured in e-CRF "Other procedure form", where adjudication is not required. PTs of Renal transplant (10038533), Renal and pancreas transplant (10052278), Renal and liver transplant (10052279) based on MedDRA v22.0.
Renal death	(5) Renal death as positively adjudicated by CEC: "Death - Non-Cardiovascular (Renal)" as the primary cause of death

AE Grouping	Criteria
EOSI not adjudicated*	
Severe hypoglycemia	Algorithm specified in Section 2.1.4.1 based on e-CRF "Hypoglycemic Events"
Genital mycotic infections	PTs in Appendix B
Urinary tract infections	PTs in Appendix B
Clinically relevant volume depletion and events related/possibly related to volume depletion	PTs in Appendix B
Diarrhea	Narrow search on "Noninfectious diarrhoea (SMQ)" [20000218] plus the following PTs (MedDRA v22.0): Gastroenteritis (10017888), Antidiarrhoeal supportive care (10055660), Enteritis (10014866), Enteritis leukopenic (10014877), Enterocolitis (10014893), Enterocolitis haemorrhagic (10014896)
Pancreatitis	PTs in Appendix B
Venous thrombotic events	PTs in Appendix B
Malignancies of special interest	Breast cancer: Narrow search on "Breast cancer: Narrow search on "Breast neoplasms, malignant and unspecified (SMQ)" [20000149] Prostate cancer: Narrow search on "Prostate neoplasms, malignant and unspecified (SMQ)" [20000152] Leydig-cell cancer: PTs of Leydig cell tumour of the testis (10024407) and Ovarian Sertoli-Leydig cell tumour (10073270) based on MedDRA v22.0 Thyroid cancer: PTs in Appendix B Renal cell cancer: PTs in Appendix B Pancreatic cancer: PTs in Appendix B Bladder cancer: PTs in Appendix B
EOSI AE leading to an amputation	
AE leading to an amputation	"AE Correction" as the reason for amputation in e-CRF "Other Procedures related to Amputation"
AE potentially leading to an amputation *	PTs in Appendix B

\* Search terms will be updated using the MedDRA version currently in effect at Covance at the time of database lock for EOSI identified by them.

\* AE potentially leading to an amputation: not belong to the EOSI list defined in protocol, the item is included and analyzed due to their relevance in regards to lower limb complications and amputations as a requirement from health authorities..

